4.5.1 Primary Efficacy Endpoint

The primary efficacy objective for this study is to evaluate the efficacy of MSTT1041A compared with placebo on the basis of the following endpoint:

Incidence of asthma exacerbations from baseline through Week 54, with asthma exacerbation defined as new or increased asthma symptoms (wheezing, coughing, dyspnea, chest tightness, and/or nighttime awakenings due to these symptoms) that result in one or both of the following:

- Hospitalization or emergency department visit with administration of systemic corticosteroid treatment
- Treatment with systemic corticosteroids for ≥ 3 days or a long-acting depot corticosteroid preparation with a therapeutic effectiveness of ≥ 3 days

The estimand of interest, i.e., the mITT estimand, is the reduction in the rate of asthma exacerbations over 52 weeks (for MSTT1041A relative to placebo) for all randomized patients who received at least one dose of study drug, regardless of adherence to the assigned study treatment or to the protocol. Because the protocol specifies that patients who discontinue study drug early continue with study assessments, an analysis of all observed exacerbation data will lead to a reasonable estimate of the mITT estimand. However, some data may be missing because of early study discontinuation, and sensitivity of the primary analysis to missing data assumptions will be assessed by sensitivity analyses per Section 4.5.4.

For each patient, the time period at risk will be defined as follows:

- From the date of randomization to date of the actual Week 54 visit for patients who completed the double-blind treatment period

- From the date of randomization to the date of last assessment during the double-blind treatment period for patients who complete or discontinue from the study early

All protocol-defined asthma exacerbations with an onset date during this time period at risk will be included in the primary analysis. For each patient, the time at risk (in years) will be computed as the duration of this time period (last day minus first day [in days] plus 1) divided by 365.25. Unadjusted rates of asthma exacerbations will be estimated by dividing the total number of protocol-defined asthma exacerbations observed during the time at risk by the total time at risk (in years) for each treatment arm.

The rate of asthma exacerbations will be compared between each active treatment arm and the placebo arm with the use of a Poisson regression model with over-dispersion. The primary analysis will be on the basis of observed exacerbations, with no imputation for premature study discontinuation. The Poisson regression model will include terms for treatment arm (three indicator variables, corresponding to the three treatment arms) and the baseline covariates described in Section 4.5. Patient time at risk will be used as an offset term in the model. The dispersion parameter will be estimated by Pearson's χ^2 statistic divided by its degrees of freedom.

Rates of asthma exacerbations adjusted for specified baseline covariates (see Section 4.5) will be estimated for each treatment arm with the use of the Poisson regression model. The ratio of exacerbation rates (for each MSTT1041A arm compared with the placebo arm) will be estimated from the Poisson regression model along with associated 95% CIs and p-values. The absolute difference in the exacerbation rates (for each MSTT1041A arm compared with the placebo arm, expressed as events per year) will also be provided, along with the associated 95% CIs.

See Sections 4.5.4, 4.5.5, and 4.5.6 for sensitivity, subgroup, and additional biomarker analyses that will be performed for the primary efficacy endpoint, respectively.

4.5.2 Secondary Efficacy Endpoints

Time to First Asthma Exacerbation

A Cox proportional hazards regression model will be used to estimate the hazard ratio comparing each MSTT1041A treatment arm with the placebo arm with respect to time to the first asthma exacerbation. The model will include treatment arm and baseline covariates as described in Section 4.5. Patients who do not experience a protocol-defined asthma exacerbation during the 52-week double-blind treatment period will be censored at the end of their time at risk (see Section 4.5.1). Point estimates, 95% CIs, and p-values for the treatment effect (MSTT1041A vs. placebo) will be calculated for each MSTT1041A dose level based on the model.

Pre-Bronchodilator Forced Expiratory Volume in 1 Second (Liters)

The absolute change in pre-bronchodilator FEV₁ from baseline will be summarized by treatment arm and timepoint. The difference in mean absolute change in pre-bronchodilator FEV₁ at Week 54 from baseline between each MSTT1041A treatment arm and the placebo arm will be estimated using a mixed model for repeated measures (MMRM). The model will use absolute change from the randomization visit as the response variable and include terms for treatment arm, study visit, treatment arm by study visit interaction, baseline FEV₁ (as a continuous variable) as well as its interaction with study visit, and the baseline covariates as described in Section 4.5. Study visit will be included as a categorical variable. An unstructured covariance matrix will be specified to model the within-subject errors. Point estimates, 95% CIs, and p-values for the treatment effect (MSTT1041A vs. placebo) will be calculated for each MSTT1041A dose level on the basis of the model for all study visits, including Week 54.

In addition to evaluating the treatment benefit at Week 54, the absolute change from baseline in pre-bronchodilator FEV₁ over time will be characterized in order to establish the time of onset of sustained FEV₁ effect. Considering each dose level separately, if a statistically significant difference between MSTT1041A and placebo is observed at Week 54, then nominal tests for significance will be performed sequentially at each prior planned timepoint for which FEV₁ was assessed (working backward), continuing until the p-value for a timepoint is ≥ 0.05 . This procedure will be used to determine the earliest timepoint at which significance is observed at that timepoint and at all subsequent timepoints up to Week 54 (comparing MSTT1041A with placebo), and considered the time of onset of sustained FEV₁ improvement.

See Sections 4.5.4, 4.5.5, and 4.5.6 for sensitivity, subgroup, and additional biomarker analyses, respectively, that will be performed for the secondary endpoint of absolute change in pre-bronchodilator FEV₁ from the randomization visit at Week 54.

Asthma Quality of Life Questionnaire (Standardized)

Asthma-specific health-related quality of life will be measured by the AQLQ(S) scores. With this scale, higher scores indicate better health-related quality of life and 0.5 points is considered the minimally important difference (MID).

The AQLQ(S) domain scores will be calculated from the individual question responses as follows:

$$\text{Symptoms} = \sum (\text{Items } 6, 8, 10, 12, 14, 16, 18, 20, 22, 24, 29, 30) / 12$$

$$\text{Activity Limitation} = \sum (\text{Items } 1, 2, 3, 4, 5, 11, 19, 25, 28, 31, 32) / 11$$

$$\text{Emotional Function} = \sum (\text{Items } 7, 13, 15, 21, 27) / 5$$

$$\text{Environmental Stimuli} = \sum (\text{Items } 9, 17, 23, 26) / 4$$

The overall health-related quality of life-score will be calculated from the individual question responses as follows and will be summarized by treatment arm and timepoint for each biomarker group.

$$\text{AQLQ(S) Overall score} = \frac{\sum (\text{Items 1 to 32})}{32}$$

The proportion of patients who achieve a clinically meaningful improvement in AQLQ(S) (improvement of ≥ 0.5 points from baseline) at Week 54 will be summarized by treatment group and timepoint. AQLQ(S) at randomization visit (Week 2) will be used as the baseline AQLQ(S) score. A logistic regression model, with terms for treatment group, baseline AQLQ(S), and the baseline covariates described in Section 4.5 will be used to compare MSTT1041A with placebo. For patients without a Week 54 assessment of AQLQ(S), the Week 26 score will be used. Patients without a post-randomization assessment (Week 26 or Week 54) will be excluded from the analysis. Point estimates, 95% CIs, and p-values for the treatment difference (MSTT1041A vs. placebo) will be calculated for each MSTT1041A dose level.

Considering each dose level separately, if a statistically significant difference between MSTT1041A and placebo is observed at Week 54, then a test for significance will be performed at Week 26. This procedure will be used to determine the earliest timepoint at which significance is observed (comparing MSTT1041A with placebo), and considered the time of onset of sustained AQLQ(S) improvement.

Asthma Control Questionnaire

Asthma control, as measured by the ACQ, will be assessed by asking patients to recall their experience with asthma during the previous week. The full ACQ consists of seven questions: five questions related to symptoms (i.e., nighttime awakening, asthma symptoms upon awakening in the morning, activity limitation, shortness of breath, and wheezing frequency), one question about use of short-acting rescue therapy, and one question about FEV₁ (to be completed by site staff). The items are scored on a scale ranging from 0 (totally controlled) to 6 (extremely poorly controlled). The items are equally weighted. For the ACQ, higher scores indicate worse control, and 0.5 points is considered the MID. The ACQ can be scored two ways: 1) the mean of the five symptom-related items (ACQ-5); or 2) the mean of all 7 items (ACQ-7).

The proportion of patients who achieve a clinically meaningful improvement in asthma control based on the ACQ-5 (decrease of ≥ 0.5 points from baseline) will be analyzed using the same methodology as described for achievement of improvement from baseline at Week 54 in AQLQ(S). ACQ-5 at randomization visit (Week 2) will be used as the baseline ACQ-5 score.

Asthma Rescue Medication Use

Asthma rescue medication use as recorded in the patient's daily electronic diary (e-Diary) will be used for analysis. For each patient, baseline asthma rescue medication use will be defined as the proportion of days with rescue medication use over a 14-day period

prior to the Week 0 visit (i.e. during screening). Patients must have two consecutive compliant weeks during screening in their asthma rescue medication use to have a baseline score calculated. During screening, a patient is compliant in a week if they have at least 5 of 7 days of non-missing entries of asthma rescue medication use. The baseline proportion of days with asthma rescue medication use will first be calculated using the two consecutive screening compliant weeks prior to the run-in visit. However, if the condition of two consecutive screening compliant weeks does not hold in the 14 days prior to the run-in visit, the window will be shifted back by 7 days until a period of two consecutive screening compliant weeks is identified. As one of the inclusion criteria for patients to enter the run-in period is completion of the e-Diary for at least 5 of 7 days during each of 2 consecutive weeks during the screening period, i.e., patients having two consecutive screening compliant weeks, missing baseline score is not expected. In the rare event that a patient does not have a valid baseline score, the patient will be excluded from this analysis.

Although rescue medication is to be recorded each morning and each evening, any day on which at least one entry is collected will be included in analyses. For each patient and monthly post-baseline assessment timepoint (i.e., Week 6, Week 10, ...Week 54), the post-baseline asthma medication use for that timepoint will be defined as the proportion of days with rescue medication use over the 28 days on or prior to the timepoint (inclusive). Patients must have recorded their asthma rescue medication use at least once a day for at least 14 days during a 28-day interval to have a score calculated for the respective timepoint. Missing entries will be excluded from the calculation. For example, if a patient has only recorded rescue medication use for 20 of the 28 days, then the proportion of days will be calculated out of the 20 days with an entry.

The absolute change from baseline in the proportion of days with asthma rescue medication use will be summarized by treatment arm and timepoint. The absolute difference in mean change in proportion of days of rescue medication use from randomization at Week 54 between each treatment arm and the placebo arm will be estimated on the basis of an MMRM analysis. The model will use absolute change from baseline as the response variable and include terms for treatment arm, study visit, treatment arm by study visit interaction, baseline asthma rescue medication use (as a continuous variable) as well as its interaction with study visit, and the baseline covariates described in Section 4.5. Study visit will be included as a categorical variable. An unstructured covariance matrix will be specified to model the within-subject errors. Point estimates, 95% CIs, and p-values for the treatment difference (MSTT1041A vs. placebo) will be calculated for each MSTT1041A dose level based on the model for all study visits including Week 54.

Asthma-Related Nighttime Awakenings

Nighttime awakenings, as recorded each morning in the patient's daily e-Diary, will be used for analysis. For each patient, the proportion of weeks without a nighttime

awakening from baseline through Week 54 will be calculated. The randomization visit (Week 2) will be used as baseline.

From the randomization visit, the subsequent weeks will be counted by a 7-day window until Week 54 is reached. For each 1-week period after randomization visit, if there are 4 or more morning diaries with missing entries, the 1-week period is considered a non-compliant week and the corresponding value will be considered as missing. These missing values will not be imputed, and these missing weeks will not be included in the denominator when calculating the proportion of weeks. However, if there are >3 morning diaries with missing entries during a 1-week period but one of the available entries for the 1-week period reports a nighttime awakening, this 1-week period will be included in the calculation.

The proportion of weeks without a nighttime awakening due to asthma will be summarized by treatment arm. The absolute difference in mean proportion between each MSTT1041A dose level and the placebo arm will be estimated on the basis of an analysis of variance model. The model will use the proportion of weeks without a nighttime awakening due to asthma as the response variable and include terms for treatment arm and the baseline covariates described in Section 4.5. Point estimates, 95% CIs, and p-values for the treatment difference (MSTT1041A vs. placebo) will be calculated for each MSTT1041A dose level.

Daytime Asthma Symptom Severity

Daytime asthma symptom severity will be assessed by patient ratings of asthma symptoms each evening, as recorded in the ADSD on their e-Diary.

The daily daytime symptom scores are calculated each day as an average of the six core evening diary symptoms: difficulty breathing, wheezing, shortness of breath, chest tightness, chest pain and cough. Each question is scored from the scale of 0 to 10, in which higher scores indicate worse symptoms. The daytime symptom score for each timepoint is then calculated as a weekly average of the 7 individual average daily scores. Daily scores will only be calculated if data for 4 or more items per day are available.

Daily scores will be averaged over the previous week prior to each scheduled visit (i.e., 7 days prior to Week 54 visit). For each week after randomization visit, if there are >3 days with missing scores out of the 7 days, the week is considered a non-compliant week and the average score for the week will be considered as missing. These missing values will not be imputed but will be handled directly by the MMRM model.

The baseline value will be derived based on a 2-week screening period prior to the Week 0 visit. Patients must have two consecutive compliant weeks during screening to have a baseline score calculated. During screening, a patient is compliant in a week if they have at least 5 of 7 days of non-missing scores. The baseline score will first be calculated using the two consecutive screening compliant weeks prior to the run-in visit.

However, if the condition of two consecutive screening compliant weeks does not hold in the 14 days prior to the run-in visit, the window will be shifted back by 7 days until a period of two consecutive screening compliant weeks is identified. Patients without a 'valid' baseline score will be excluded from the analysis.

The absolute change from baseline in daytime symptom severity scores will be summarized by treatment arm and timepoint. The absolute difference in mean change in daytime symptom severity scores from baseline at Week 54 between each treatment arm and the placebo arm will be estimated on the basis of an MMRM analysis. The model will use absolute change from baseline as the response variable and include terms for treatment arm, study visit, treatment arm by study visit interaction, baseline symptom score as well as its interaction with study visit, and the baseline covariates described in Section 4.5. Study visit will be included as a categorical variable. An unstructured covariance matrix will be specified to model the within-subject errors. Point estimates, 95% CIs, and p-values for the treatment difference (MSTT1041A vs. placebo) will be calculated for each MSTT1041A dose level based on the model for all study visits including Week 54.

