4.5.6.1 Asthma Control Questionnaire

Asthma control, as measured by the Asthma Control Questionnaire (ACQ) (Juniper et al. 1999b), will be assessed by asking patients to recall their experience with asthma during the previous week. The full ACQ consists of seven questions: five questions related to symptoms (i.e., nighttime awakening, asthma symptoms upon awakening in the morning, activity limitation, shortness of breath, and wheezing frequency), one question about use of short-acting rescue therapy, and one question about FEV₁ (to be completed by site staff). The items are scored on a scale ranging from 0 (totally controlled) to 6 (extremely poorly controlled). The items are equally weighted. The ACQ can be scored three ways: 1) the mean of the five symptom-related items (ACQ-5); 2) the mean of the five symptom-related items plus the short-acting rescue use item (ACQ-6); or 3) the mean of all 7 items (ACQ). The ACQ has strong measurement properties for use in both clinical practice and clinical trials. The ACQ-5 is part of the eligibility criteria and will be administered at the screening and run-in visits. The ACQ will be administered at the randomization visit, Week 26, and Week 54.

A copy of the ACQ is provided in [Appendix 5](#).

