4.5.6.2 Standardized Asthma Quality of Life Questionnaire

The Standardized Asthma Quality of Life Questionnaire (AQLQ[S]) will be used to assess the patients' asthma-specific health-related quality of life (Juniper et al. 1999a). The 32-item questionnaire contains four domains: activity limitations, symptoms, emotional function, and environmental stimuli. The AQLQ(S) has a recall specification of 2 weeks. Items are scored on a 7-point scale ranging from 1 (severe impairment) to 7 (no impairment). A copy of the AQLQ(S) is provided in [Appendix 6](#). The AQLQ(S) will be administered at the randomization visit, Week 26, and Week 54.

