4.5.4 Sensitivity Analyses

Sensitivity analyses will be performed to evaluate the robustness of the primary analysis results.

- **Parametric Model.** The primary efficacy endpoint will be re-analyzed using a negative binomial regression model, using the same covariates as specified for the primary analysis with Poisson regression. All other elements of the analysis will remain the same as in the primary analysis.

The following analyses will be performed to assess the sensitivity of results to missing data assumptions:

- **Missing Data Assumptions.** The primary endpoint (incidence of asthma exacerbations) and all secondary efficacy endpoints (except for time to first asthma exacerbation) found to be significant for a given MSTT1041A arm will be re-analyzed assuming that missing data is missing not at random, rather than missing at random (MAR), via tipping point sensitivity analyses implemented using multiple imputation. In general, imputation models will account for the same baseline covariates as used in the earlier described analysis of the endpoint and post-baseline outcome data when possible. Multiple imputed datasets will be grouped by a range of missing data assumptions and analyzed according to the same analysis models specified in Section 4.5, and the results will be combined for each assumption using Rubin's rules (Barnard and Rubin 1999). These analyses will be implemented as follows:

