early. An event count corresponding to each unobserved period will be imputed by first fitting a negative binomial generalized linear model to the observed data and sampling from the posterior distribution of the model parameter estimates. These sampled parameter estimates along with the patient-specific observed covariate values, observed exacerbation counts, and length of unobserved interval will be used in conjunction with a random number generator to impute an event count for the unobserved time period, which is added to the observed event count (Keene et al. 2014). These augmented datasets will be analyzed according to the model described in Section 4.5.1 and the results combined using Rubin's rules.

- In the tipping point sensitivity analysis, the underlying event rate used to impute unobserved event counts for a given arm will be adjusted via a multiplier delta; a separate delta will be applied to each arm. A range of delta values will be used to adjust the underlying event rate used for imputation in the MSTT1041A and placebo arms independently based on a grid of delta adjustments. The delta values will be chosen on the basis of the treatment effect (rate ratio) observed for a given MSTT1041A arm compared with placebo from the analyses described in Section 4.5.1. The range of delta values will include cases where dropouts from the MSTT1041A arm are assumed to have worse outcomes than dropouts from the placebo arm. For each endpoint, the resulting point estimates of treatment effect and corresponding p-values under each pair of deltas for each MSTT1041A and placebo comparison will be tabulated.

Also, for the secondary endpoint (absolute change from baseline in FEV₁), a cumulative responder plot which displays, by treatment arm, the proportion of patients who achieve each specified absolute change in pre-bronchodilator FEV₁ from baseline at Week 54 for a range of possible FEV₁ changes will be provided. For this plot, patients with missing Week 54 data will be assumed to be non-responders.

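### The Week 54 ACQ-5 and AQLQ(S) responder analyses carry the Week 26 score forward and drop patients with neither score; multiple imputation of the Week 54 score should be the main analysis.

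*SAP*

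**What the plan says.** SAP section 4.5.2 analyses the proportion of patients with AQLQ(S) "improvement of ≥ 0.5 points from baseline" at Week 54 by logistic regression. Its missing-data rule has two parts: "For patients without a Week 54 assessment of AQLQ(S), the Week 26 score will be used", and "Patients without a post-randomization assessment (Week 26 or Week 54) will be excluded from the analysis". The ACQ-5 paragraph of the same section adopts the method, and section 4.5.3 does so for SGRQ and ACQ-7. Section 4.8 refers back to these rules.

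The substitute is always 28 weeks older than the value it replaces. Protocol section 4.5.6.2 states "The AQLQ(S) will be administered at the randomization visit, Week 26, and Week 54", and section 4.5.6.1 states "The ACQ will be administered at the randomization visit, Week 26, and Week 54". Protocol Appendix 1 shows neither questionnaire at the early termination visit. SAP section 4.5 also sets a Week 54 visit made after its window to missing, so those patients fall back on Week 26 too.

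Both endpoints are in the fixed testing sequence of SAP Table 1, at two-sided 5%: ACQ-5 is secondary number 3 and AQLQ(S) number 7. Section 4.5.4 promises a tipping-point analysis by multiple imputation for secondary endpoints found significant, other than time to first exacerbation. The steps it gives are for continuous changes from baseline and for exacerbation counts.

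**The concern.** The endpoint is response at Week 54, but the estimate is a weighted mixture of Week 54 response and, for later leavers, Week 26 response. The weights depend on how many patients leave and when. The logistic model treats a carried value as a real Week 54 observation, so its standard error takes no account of the substitution. Patients lost before Week 26 leave the analysis altogether, although section 4.5 calls for efficacy analyses in the mITT population.

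The ACQ-5 result decides whether secondaries 4 to 7 can be formally tested, so an error there carries down the sequence. The planned follow-up test at Week 26, used to date sustained AQLQ(S) improvement, also reuses the carried patients' scores: the same value enters both tests.

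The safeguard is partial. If the rule costs an endpoint its significance, no tipping-point analysis is triggered. If the endpoint is significant, the SAP does not say how a delta acts on a yes/no outcome.

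**Working it through.** **Inputs from the documents.** The carried score is 54 − 26 = 28 weeks old. The SAP reports 502 patients randomised 1:1:1:1 (125.5 per arm) and assumes 15% dropout (section 2.2). If all of that became missing Week 54 scores, 0.15 × 125.5 ≈ 19 patients per arm would be affected. The plan states no response rate, power or missing-data figure for these endpoints, so there is no figure of its own to reproduce. Everything below is assumed.

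**Formula.** In one arm, let d1 be the share lost before Week 26 and d2 the share lost between Weeks 26 and 54. Let p be completers' Week 54 response, r26 the later leavers' Week 26 response, and q1 and q2 the true Week 54 response of early and later leavers.

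- SAP rate: S = [(1 − d1 − d2)p + d2·r26]/(1 − d1)
- True rate: (1 − d1 − d2)p + d1·q1 + d2·q2
- Bias in that arm: d1(S − q1) + d2(r26 − q2)

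The first term comes from exclusion and the second from carry-forward. The treatment contrast is biased by the active-arm value minus the placebo value.

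**Simulation.** Two million patients per arm; improvement scores with SD 1, a 0.5-point threshold and correlation 0.6 between visits. Half of the losses occur before Week 26, at random. The rest occur after Week 26 and are more likely with a poor Week 26 score.

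- A: mean improvement 0.6 in both arms at both visits.
- B: as A, but leavers worsen to a mean of 0.1.
- C: active mean 0.9 against 0.6 at both visits; active leavers fall back to 0.6.
- D: active mean 0.75 at Week 26 and 0.9 at Week 54, kept after leaving; placebo 0.6.

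Bias of the SAP rule in the Week 54 responder difference, in percentage points:

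| Dropout active/placebo | A | B | C | D |
|---|---|---|---|---|
| 15%/15% | 0.0 | 0.0 | +1.6 | −0.6 |
| 20%/10% | −0.7 | +1.1 | +1.5 | −1.4 |
| 10%/20% | +0.7 | −1.1 | +1.8 | +0.3 |
| 25%/5% | −1.4 | +2.2 | +1.4 | −2.4 |
| 5%/25% | +1.4 | −2.3 | +1.9 | +1.2 |

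**Hand check of D at 15%/15%, with loss fully random.** Active response is Φ(0.25) = 59.9% at Week 26 and Φ(0.40) = 65.5% at Week 54; placebo is constant. The carried weight is 0.075/0.925 = 0.081, and 0.081 × (59.9 − 65.5) ≈ −0.5 points. This is near the simulated −0.6, where loss depends on the Week 26 score.

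**What imputation does.** In A and D, loss depends only on the observed Week 26 score, so it is missing at random. Imputing the Week 54 score by arm from the Week 26 score brings the bias to about zero. In B and C, leavers change after their last observation. Imputation under missing at random cannot see this, and under unequal dropout in B it leaves a larger bias than carry-forward.

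**The case against.** The strongest objection concerns size. A reader might assume that every lost patient is a Week 54 non-responder and infer an error of several points. Take completers at 60% and 50%, later leavers at 50% and 40% at Week 26, half of losses before Week 26, and dropout of 20% and 10%. The SAP rule gives (0.48 + 0.05)/0.90 − (0.45 + 0.02)/0.95 = 58.9% − 49.5% = 9.4 points. The truth is 0.48 − 0.45 = 3.0 points. That gap does not show a fault of carry-forward. Missing-at-random imputation in the same set-up gives 9.4 to 10.0 points, no closer to the truth. The gap comes from assumed informative loss, on a dropout split that the documents do not give.

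Other tempting readings also go too far:

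- **Unequal dropout as the condition.** It is not necessary: C at 15%/15% gives +1.6. It is not always sufficient: if leavers respond like completers at both visits, the bias is zero at any split.
- **No missing-at-random analysis anywhere.** Section 4.5.4 starts from imputation under that assumption for significant secondaries. The gap is that its steps stop short of binary responders.
- **A contradiction with the FEV₁ responder plot**, where "patients with missing Week 54 data will be assumed to be non-responders". That plot is supplementary; the FEV₁ test itself uses a repeated-measures model.
- **A breach of the stated estimand.** The mITT estimand in section 4.5.1 is written for the primary endpoint only.

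One mitigating point stands. Protocol section 4.6.2 asks patients who stop study drug to continue all assessments, and the SAP uses those data. Missing scores should therefore come mainly from study withdrawal and out-of-window visits.

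**Conclusion.** The point holds as a cheap improvement to two alpha-controlled secondary endpoints and, by reference, two exploratory ones. The rule estimates a mixture of Week 26 and Week 54 response and understates the uncertainty from missing scores. Unless the errors in the two arms cancel, it is biased when response moves after Week 26 or leavers differ from completers.

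Under the assumed scenarios, averaging 15% dropout, the bias is about 0 to 2.4 percentage points with either sign. The direction cannot be fixed in advance, and the documents do not show that bias will occur. Missing-at-random imputation removes the part due to replacing Week 54 by Week 26 when loss depends on observed data. It does not remove informative loss, so the tipping-point step has to be workable for these endpoints.

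**What to change.** Change SAP sections 4.5.2, 4.5.3 and 4.5.4 before the Week 54 analysis, since SAP section 1 bars changes from that point:

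1. Make the main responder analysis multiple imputation of the continuous Week 54 score under missing at random, by arm. Use the baseline score, Week 26 score, model covariates and available daily ADSD scores. Diary data to the point of leaving allow patients lost before Week 26 to stay in the analysis.
2. Dichotomise each imputed dataset at 0.5 points (4 points for SGRQ), fit the planned logistic model and combine with Rubin's rules.
3. Apply the tipping-point deltas to the imputed continuous scores before dichotomising.
4. Keep the Week 26 carry-forward rule as a sensitivity analysis.

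Counting all missing patients as non-responders should not become the main analysis: in the four scenarios at 20%/10% dropout its bias was −2.7 to −6.8 points.

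The cost is SAP text, a little more programming with a technique section 4.5.4 already uses, and slightly wider intervals. Adding questionnaires at the early termination visit is not recommended. It needs a protocol amendment after 502 patients have been randomised, and a score taken four weeks after the last dose is not, in general, a Week 54 score.
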